## 9 STATISTICAL METHODOLOGY

Initially ten patients will be treated to determine the feasibility of HIVM for peritoneal carcinomatosis. This first part of the study is a pilot study of feasibility. If seven or more patients are deemed a success by meeting all of the criteria below, then HIVM will be deemed feasible in the study of peritoneal carcinomatosis. Criteria include the ability to complete each of the following:

1. Identify and measure vessels associated with peritoneal tumor implants
2. Determine vessel density per 10x field
3. Visualize vital dyes within the vessels [fluorescein and indocyanine green (ICG)]
4. Calculate the blood flow velocity of the vessels and tissue penetration of fluorescein and ICG as markers of vessel permeability.

If the true success rate is 60%, the probability of deeming HIVM feasible is 63%; if the true success rate is 70%, then the probability of deeming HIVM feasible is 88%; and if the true success rate is 90%, then the probability of deeming HIVM feasible increases to 99%.

If HIVM is deemed feasible, then an additional 20 patients will be accrued to this study in order to address the following:

1. Post-operative comparison of the microvasculature of peritoneal carcinomatosis with normal tissue (peritoneum) in each individual subject using vessel diameters, vessel density, detection of intravital dye and flow rates.
2. Post-operative correlation of the microvasculature with pathologic features of the tumor implants (i.e. tumor grade) at the time of the final pathology report (5-7 days after surgery).
3. Post-operative correlation of the microscopic observation of the tumor microvasculature tumor-specific and overall survival.

An abnormal HIVM observation is defined by any of the following criteria:

1. Aberrant vessel structure compared to normal tissue, which includes tortuosity of the vessel wall or a closed loop formation.
2. Aberrant vessel branching patterns compared to normal tissue, which includes erratic and disorganized branching points.
3. Blood vessel density that is less than or greater than one standard deviation of the blood vessel density observed in normal tissue.
4. Inability to detect flow or intravital dye within a vessel.
5. Average blood flow rate through observed vessel that is less than one standard deviation of the average blood flow rate through a normal vessel.

A matched analysis will be performed for observations of microvasculature between the peritoneal tumor implants and normal tissue. For dichotomous variable comparisons between vessel structure (normal vs aberrant), vessel branching patterns (normal vs aberrant), or detection of intravital dye (present vs absent), a McNemar's test will be performed. For continuous variable comparisons between blood vessel density and average blood flow rate, a paired t test will be performed.

Associations between characteristics for the baseline (normal peritoneal microvasculature observed surrounding the tumor implant site) and tumor implant itself will be depicted with graphics, correlations, and model results.

Adverse event and complication rates will be described using upper one-sided 95% Clopper Pearson confidence limits.

Overall survival will be defined as the duration of time from diagnosis to time of death. Disease specific survival will be defined as the time from CRS-HIPEC to death due to recurrence. Overall survival and disease specific survival will be generated using standard Kaplan-Meier methodology.

A maximum of 30 subjects will be enrolled in this study (initially 10 to determine feasibility and then 20 additional subjects if deemed feasible). The accrual rate is estimated at one subject per month, and the estimated study duration is 30 months.

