**Objectives:**

*Primary objective(s):* To determine the feasibility of performing HIVM in patients with peritoneal carcinomatosis during standard course of treatment (cytoreductive surgery with

hyperthermic intraperitoneal chemotherapy, or CRS-HIPEC). A successful intravital microscopic observation will include the ability to complete each of the following:

1. Identify and measure vessels associated with peritoneal tumor implants
2. Determine vessel density per 10x field
3. Visualize vital dyes within the vessels [fluorescein and indocyanine green (ICG)]
4. Calculate the blood flow velocity of the vessels and tissue penetration of fluorescein and ICG as markers of vessel permeability.

*Secondary objective(s):*

1. Compare the microscopic observation of the tumor-associated vessels with normal tissue (peritoneal surface) in each individual subject.
2. Correlate the microscopic observations of the tumor-associated vessels with pathologic grade of tumor implants.
3. To correlate the microscopic observation of the microvasculature with tumor-specific and overall survival.

**Study Design:** This is a non-randomized, single center, study of HIVM observation in subjects with peritoneal carcinomatosis undergoing CRS-HIPEC.

All subjects will meet the inclusion and exclusion criteria prior to participation in this study. Standard evaluation by the Preoperative Anesthesia clinic at Mayo Clinic Florida may include additional testing such as EKG, chest x-ray, and/or pulmonary function tests.

The study will be performed in two parts. Part 1 will enroll 10 patients with an expected feasibility rate of 70%. Whereas the feasibility rate in primary melanoma was 90%, the expected feasibility rate for the peritoneal surface may be lower as the site is in an anatomically deeper location. If Part 1 is not met (i.e. in three or more patients), the primary objective would not be considered technically feasible, and then the study will be stopped. If Part 1 is fulfilled, then the study will continue with an additional 20 patients enrolled (total of 30 patients). Accrual is expected to take 2.5 years.

*Inclusion criteria:*

1. Age  $\geq$  18 years of age.
2. ECOG Performance Status of  $\leq 2$ .
3. Measurable tumor on the peritoneal surface by direct visualization requiring surgical resection in the OR.

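### Part I has no clear rule that stops accrual once its feasibility threshold can no longer be reached

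*Combined protocol and SAP*

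**What the plan says.** Section 9 sets the size of Part I: "Initially ten patients will be treated to determine the feasibility of HIVM for peritoneal carcinomatosis". Its decision rule reads: "If seven or more patients are deemed a success by meeting all of the criteria below, then HIVM will be deemed feasible". It describes no look at the count before ten patients and no action when seven successes become impossible.

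The Synopsis (Study Design) does contain a stop statement: "If Part 1 is not met (i.e. in three or more patients), the primary objective would not be considered technically feasible". The consequence it attaches is that the trial ends. It does not say what is counted in those three or more patients, or whether the count is applied as patients accrue or only after the tenth.

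Other parts of the protocol bear on this:

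- Section 4.2: microscope malfunction and unrelated surgical events that end the operation are not failures, and those patients are replaced. Measurements are made off-line from recorded video.
- Section 8: the DSMB reviews the study once a year.
- Section 9: accrual is estimated at one subject per month.
- Section 12.2: the investigators or the sponsor may terminate the study for reasonable cause.

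**The concern.** Under seven of ten, three failures still pass and four cannot. Any Part I patient treated after the fourth counted failure has a skin-prick test, two intravenous dyes and intraoperative imaging, and none of it can alter the feasibility verdict. The procedure is not therapeutic. The protocol describes the dye risk as low but not nil: Section 1.2.2 cites fluorescein reactions from just over 1% in a more recent series to 5–10% historically, and Sections 1.2.2 and 1.4.2 mention rare severe reactions and deaths with the two dyes.

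No other provision clearly fills the gap. Ten patients at one per month take about ten months. If the annual DSMB review is counted from the start of accrual, it falls after Part I is full. The termination clause is discretionary. Because Section 4.2 removes equipment and unrelated surgical problems from the failure count, most counted failures should reflect the method itself, which is the signal Part I exists to detect.

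**Working it through.** **Inputs.** Part I size n = 10 and threshold of seven successes (Section 9). The Synopsis gives the expected rate: "Part 1 will enroll 10 patients with an expected feasibility rate of 70" per cent. Section 9 also considers true rates of 60% and 90%. The 50% rate below is a reviewer assumption that shows the range. Patients are treated as independent with a common success rate p.

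**The plan's own figures.** Section 9 states 63%, 88% and 99% for the probability of deeming HIVM feasible at true rates of 60%, 70% and 90%; the first reads "If the true success rate is 60%, the probability of deeming HIVM feasible is 63" per cent. The exact tail P(X ≥ 7), X ~ Binomial(10, p), gives 38.2%, 65.0% and 98.7%. Only the last agrees. The 63% matches six or more of ten at 60% (63.3%), and the 88% matches seven or more of ten at 80% (87.9%). This is a separate defect. The work below uses the rule as written, not the stated percentages.

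**When the verdict is fixed.** With seven successes needed from ten, at most 10 − 7 = 3 failures are allowed. The fourth failure decides.

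**Chance of treating someone after that point.** This requires four or more failures among the first nine patients:

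P = 1 − Σ(j = 0 to 3) C(9, j)(1 − p)^j p^(9 − j)

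**Mean number treated after that point.** Patient m + 1 is surplus if the first m patients already contain four failures, so the mean is the sum of P(at least four failures in the first m) over m = 4 to 9:

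- p = 0.7: 0.0081 + 0.0308 + 0.0705 + 0.1260 + 0.1941 + 0.2703 = 0.700
- p = 0.6: 0.0256 + 0.0870 + 0.1792 + 0.2898 + 0.4059 + 0.5174 = 1.505
- p = 0.5: 0.0625 + 0.1875 + 0.3438 + 0.5000 + 0.6367 + 0.7461 = 2.477

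Dividing by the probability of a negative verdict gives the mean among negative verdicts: 0.700/0.3504 = 2.0, 1.505/0.6177 = 2.4 and 2.477/0.8281 = 3.0.

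| True rate | P(feasible), with or without the stop | P(at least one surplus patient) | Mean surplus, all outcomes | Mean surplus, given negative verdict | Expected Part I size with the stop |
|---|---|---|---|---|---|
| 50% (assumed) | 17.2% | 74.6% | 2.5 | 3.0 | 7.5 |
| 60% | 38.2% | 51.7% | 1.5 | 2.4 | 8.5 |
| 70% | 65.0% | 27.0% | 0.7 | 2.0 | 9.3 |
| 90% | 98.7% | 0.8% | 0.02 | 1.4 | 10.0 |

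The most that can be spared is 10 − 4 = 6 patients, if the first four all fail.

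**Why P(feasible) does not move.** The stop acts only on sequences that already contain four failures. Each of these would be a negative verdict at ten patients anyway.

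**If the Synopsis wording means failures.** Three failures would then end the study, which amounts to requiring eight of ten. P(feasible) becomes 16.7%, 38.3% and 93.0% at 60%, 70% and 90%, and the expected Part I size with a stop at the third failure is 7.0, 8.1 and 9.9. Exactly three failures in ten is a pass in Section 9 and a stop in the Synopsis. Stopping at the third failure while keeping seven of ten would therefore change the verdict. The neutrality shown above holds only when the stop and the threshold match.

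**The case against.** The strongest reply is that a stop may already exist. A failure count followed by a statement that the study will be stopped can be read as a running rule, in which case accrual is already curtailed. A reader might infer from Section 9 that all ten patients will certainly be treated whatever happens. The documents do not support that as fact, because the Synopsis leaves the timing open. The gap that stands is that no passage clearly says accrual ends during Part I, and the one stop statement conflicts in count with Section 9.

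A reader might also infer that surplus patients spend extra time under anesthesia. Section 4.2 puts the observation at 15–20 minutes, has other surgical steps continue meanwhile, and does not expect the operation to be significantly lengthened. No added anesthesia time should be claimed.

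Three further points have weight:

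- The mean saving is only 0.7 patients at the expected 70%, and the larger savings need rates of 50% or below, which the documents do not posit.
- Completing a ten-patient pilot is a defensible choice. Later patients still inform the success rate, which of the four components fails, and the adverse-event limits in Section 9.
- One subject per month is an estimated average, not a minimum spacing, and no turnaround is given for the off-line analysis, so two cases could fall close together.

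These limit the size of the point and raise its cost a little. They do not supply the missing rule.

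**Conclusion.** The point stands as a cheap improvement, not as an error that invalidates the design. Section 9 provides for ten treated patients without a stop at the deciding failure, and the Synopsis wording neither fills that gap nor agrees with the seven-of-ten rule.

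If accrual does run to ten, the chance that at least one patient is dosed with no bearing on the verdict is about one in four at the protocol's expected rate and about one in two at 60%. The benefit lies mainly in the scenarios where HIVM works poorly at this site. The Synopsis itself allows that feasibility may be lower at a deeper location, and Section 1 says the technique has not been studied in this setting.

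The figures rest on independent patients with a constant success rate, on seven of ten as written, and on each case being classified before the next patient is dosed. The 50% row is an assumption.

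**What to change.** First, reconcile the count in the Synopsis with the threshold in Section 9, and say in the Synopsis what is counted. Which count is intended is for the sponsor to decide.

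Then add to Section 9, in substance: Part I accrual ends as soon as the number of counted failures, after the exclusions and replacements in Section 4.2, makes the reconciled feasibility threshold unattainable. Each patient's video is classified as success, failure or replaced before the next patient is dosed. Under seven of ten this is the fourth failure; under eight of ten, the third. Report the Part I success rate with an interval that allows for the stopping rule.

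The cost is a few sentences and prompt scoring of each video. The planned one patient per month should allow this, although two closely scheduled operations would need the second observation to wait for the first classification. If Part I ends early, the success rate is less precise, and there is less information on the individual components and on adverse events. For the chosen threshold, the probability of declaring HIVM feasible is unchanged.

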Technical difficulties with the microscope apparatus (e.g. malfunction of the software or structural damage to any of the microscope components) or unforeseen events during the course of surgery that are unrelated to the study intervention but that result in the termination of the surgery (e.g. adverse reaction to anesthetic prior to administration of intravital dye or hemodynamic instability from a complication of the surgery) will not be considered failures of the primary objective. In these circumstances, the subject will be considered to be off-study and be replaced with a subsequent patient.

Off-line analysis of digitally recorded live video will be performed using parameters and statistical methods that have been developed in our preclinical imaging studies.[1] Lumenal cross-sectional diameter (D) of vessels and velocity (V) of dye labeled cells will be measured in off-line observations. Wall shear rate ( $\gamma$ ) will be calculated as  $8(V \div D)$ .[92] Vessel density will be determined by measuring the calculated blood vessel area as a percent of the total visual field area. If visible, the uptake of fluorescein or ICG will be measured as a diffusion rate (distance from tumor vessel over time) and as a percent of the total tumor field observed (percent of visual field expressed as surface area with dye detected). Blood flow velocity will be determined by the equation  $Q = (RBC \text{ velocity}/1.6) \times (d/2) \times \pi$ .

These data will be calculated and recorded in a spread sheet that will also be saved onto a password-protected hard drive in the Principal Investigator's laboratory. Additionally, all data will be de-identified and provided to the Biostatistician. Generated data and the raw video images will be stored for review at any time to satisfy any audit of the collected data. This saved data will readily allow the determination of a successful observation including the identification of tumor vessels, the associated vessel measurements, vessel density, and dye enhanced imaging acquisition.

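### The stated chances of declaring HIVM feasible in Part I (63% and 88%) do not follow from the 7-of-10 rule, which gives 38% and 65%

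*Combined protocol and SAP*

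**What the plan says.** Section 9 (Statistical Methodology) fixes the Part I sample size: "Initially ten patients will be treated to determine the feasibility of HIVM for peritoneal carcinomatosis". It also fixes the decision rule: "If seven or more patients are deemed a success by meeting all of the criteria below, then HIVM will be deemed feasible". It then gives three probabilities of passing:

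- "If the true success rate is 60%, the probability of deeming HIVM feasible is 63" percent
- "if the true success rate is 70%, then the probability of deeming HIVM feasible is 88" percent
- "if the true success rate is 90%, then the probability of deeming HIVM feasible increases to 99" percent

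The Synopsis (Study Design) gives the planning value: "Part 1 will enroll 10 patients with an expected feasibility rate of 70" percent. If Part I passes, 20 more patients are enrolled; if not, the study stops. The plan gives no other operating characteristics, null rate or error limits for this decision.

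**The concern.** With a fixed number of patients and a fixed cut-off, the chance of passing is a binomial tail probability that anyone can check. Two of the three stated figures look far too high for a cut-off of seven in ten. At a true rate of 70% the expected number of successes is exactly seven, so the chance of reaching seven cannot be close to 90%.

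These figures are the whole quantitative justification for the primary decision rule. If they are wrong, an ethics committee or the data and safety monitoring board would think a failed Part I is unlikely at the expected rate. They could then read such a failure as stronger evidence against the technique than it is. The 60% row errs in the same direction: it overstates how often the study goes on at a rate below the expected one.

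**Working it through.** **Inputs**

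- Sample size n = 10 and cut-off of 7 or more successes: Section 9.
- True rates of 60%, 70% and 90%, with stated probabilities of 63%, 88% and 99%: Section 9.
- Expected rate of 70%: Synopsis, Study Design.
- Patients lost to microscope malfunction or unrelated surgical events are replaced ("In these circumstances, the subject will be considered to be off-study and be replaced with a subsequent patient", Section 4.2), so the denominator stays at ten evaluable patients.

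**Formula**

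P(X ≥ 7) = Σ C(10, k) p^k (1 − p)^(10 − k), summed over k = 7 to 10.

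**Attempt to reproduce the plan's figures**

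| True rate p | k = 7 | k = 8 | k = 9 | k = 10 | P(X ≥ 7) | Stated | Stated minus exact |
|---|---|---|---|---|---|---|---|
| 0.60 | 0.21499 | 0.12093 | 0.04031 | 0.00605 | 0.3823 | 63% | +24.8 points |
| 0.70 | 0.26683 | 0.23347 | 0.12106 | 0.02825 | 0.6496 | 88% | +23.0 points |
| 0.80 | 0.20133 | 0.30199 | 0.26844 | 0.10737 | 0.8791 | not given | – |
| 0.90 | 0.05740 | 0.19371 | 0.38742 | 0.34868 | 0.9872 | 99% | agrees on rounding |

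The 90% row reproduces. The 60% and 70% rows do not.

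**Stopping probability at the expected rate**

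From the plan's figure: 1 − 0.88 = 0.12. From the rule as written: 1 − 0.6496 = 0.3504, or about one time in three.

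**Could another rule or method explain the figures?**

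| Rule or method | p = 0.60 | p = 0.70 | p = 0.90 |
|---|---|---|---|
| Stated in the plan | 63% | 88% | 99% |
| 6 or more of 10, exact | 63.3% | 85.0% | 99.8% |
| 7 or more of 10, exact | 38.2% | 65.0% | 98.7% |
| 8 or more of 10, exact | 16.7% | 38.3% | 93.0% |
| 7 or more of 10, normal approximation | 25.9% | 50.0% | 98.3% |
| Same, with continuity correction | 37.3% | 63.5% | 99.6% |

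None of these matches all three stated figures. Across every n from 5 to 30 and every cut-off, no single rule gives both 63% at p = 0.60 and 88% at p = 0.70 to the whole percent. The only one within two points of both is 10 or more of 17 (64.1% and 89.5%), which is not this design.

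**Possible source (inference; the documents do not say)**

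63% equals P(X ≥ 6) at p = 0.60 (0.6331), and 88% equals P(X ≥ 7) at p = 0.80 (0.8791). The first figure may come from the wrong cut-off and the second from the wrong true rate.

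**The case against.** The arithmetic cannot be contested, but three points can be made on the other side.

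- **The cut-off is not settled.** The Synopsis says "If Part 1 is not met (i.e. in three or more patients), the primary objective would not be considered technically feasible", and the study then stops. Read literally, three failures end the study, so eight successes are needed. Exactly seven successes would pass under Section 9 and stop under the Synopsis. With eight as the cut-off, the probabilities are 17%, 38%, 68% and 93% at true rates of 60%, 70%, 80% and 90%, and the stopping probability at 70% is about 62%. This stands as a reason to reconcile the two places in the same edit. It does not rescue the stated figures, which are further from this reading than from the other.
- **The intent is unknown.** The documents do not say whether the rule or the probabilities express what the team wanted. If about 88% at a 70% rate was a requirement, seven of ten does not deliver it, and correcting the text alone would not be enough. This stands as a question for the sponsor.
- **The practical effect is limited.** This is a ten-patient pilot with no hypothesis test. The decision follows the observed count, and the wrong figures alter no patient's classification. The plan gives 70% as an expected rate, not as a formal target, so a stop at that rate is not an error in a defined sense. That is fair. Even so, misstatements of 23 to 25 points in the only figures offered for the primary decision need correcting.

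**Conclusion.** Wrong as written, and it must be fixed. Under the rule in Section 9, the probability of declaring HIVM feasible is 38% at a true rate of 60% (stated 63%) and 65% at 70% (stated 88%). The 99% at a true rate of 90% is correct. At the protocol's own expected rate, the chance of stopping after Part I is about 35%, not 12%.

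The result assumes ten evaluable patients, independent outcomes with a common success rate, and the cut-off of seven or more. Replacing patients after technical or unrelated events does not change it, because the rates then apply to the ten evaluable patients.

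**What to change.** In Section 9, replace the sentence giving the three probabilities. Suggested wording: *Under the rule of at least seven successes in ten patients, the probability of deeming HIVM feasible is 38%, 65%, 88% and 99% if the true success rate is 60%, 70%, 80% and 90%, respectively. At the expected rate of 70%, the probability of stopping after Part I is 35%.*

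In the same edit, reconcile the Synopsis stopping wording with Section 9 so that exactly seven successes leads to one decision only. The values above hold only if the confirmed cut-off is seven or more; for any other cut-off they must be recalculated.

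The cost is one sentence in Section 9 and the matching clause in the Synopsis. Correcting the text needs no change in sample size, endpoint or analysis, but the figures become less favourable. If the sponsor finds a 35% chance of stopping at the expected rate unacceptable, the rule itself would have to be revisited, which is a separate design decision.

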## 4 METHODOLOGY

### 4.1 Study Design

This is an open-label, non-randomized, single center, study of IVM observation in conjunction with fluorescein and ICG in subjects with peritoneal carcinomatosis undergoing CRS-HIPEC. The first part is a Pilot study of feasibility.

Subjects will be treated on an inpatient basis. All subjects will meet the inclusion and exclusion criteria summarized in **Section 5.1** and **Section 5.2** prior to participation in this study. Standard evaluation by the Preoperative Anesthesia clinic may include additional testing such as EKG, chest x-ray, and/or pulmonary function tests, but this is performed based upon their established guidelines. If any of these tests preclude a wide excision in the operating room, then the patient is excluded from this study.

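### Aberrant structure and branching are defined relative to the tissue they are then McNemar-tested against, with no scoring rule for the normal field and no masking of the reader, so the test may reject without a true difference

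*Combined protocol and SAP*

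**What the plan says.** Section 9 lists what makes an observation abnormal. Criterion 1 is "Aberrant vessel structure compared to normal tissue, which includes tortuosity of the vessel wall or a closed loop formation". Criterion 2 is "Aberrant vessel branching patterns compared to normal tissue, which includes erratic and disorganized branching points". Both are worded relative to normal tissue, and both then name morphological features.

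The analysis follows in the same section: "A matched analysis will be performed for observations of microvasculature between the peritoneal tumor implants and normal tissue". The plan next names its test for the binary features. "For dichotomous variable comparisons between vessel structure (normal vs aberrant), vessel branching patterns (normal vs aberrant") and for dye detection, "a McNemar's test will be performed". The comparator is described as the "baseline (normal peritoneal microvasculature observed surrounding the tumor implant site").

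On reading, Section 4.2 says "Off-line analysis of digitally recorded live video will be performed", using methods from the group's preclinical work. Section 4.1 says "This is an open-label, non-randomized, single center, study of IVM observation". De-identification is mentioned only for data going to the biostatistician.

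The plan does not state:
- whether or how the normal field is itself rated normal or aberrant;
- whether normal tissue means the patient's paired field or a general standard;
- whether the reader is kept from knowing which tissue is on screen;
- the alpha level, the version of McNemar's test, or any expected discordance.

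**The concern.** McNemar's null hypothesis is that discordant pairs fall equally often in each direction. That is meaningful only if both members of a pair are rated by one rule. If the normal field is the yardstick for rating the implant, it cannot be aberrant relative to itself. One discordant cell is then empty, and the null can be true only if no implant is ever called aberrant.

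Masking is a separate route to the same bias. Disorganised branching is a judgement, the Background section leads a reader to expect abnormal tumor vessels, and nothing described keeps the tissue label from the reader.

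At stake is whether a significant structure or branching result could be read as a real difference between implant and normal peritoneum. Section 3.2 makes the tumor-normal comparison the first secondary objective.

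**Working it through.** The plan gives no operating characteristic for these tests, so there is no figure to reproduce.

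**Inputs from the plan.** 20 patients in Part II and at most 30 in total (Section 9). The plan does not say whether Part I patients enter these comparisons, so both numbers of pairs are shown.

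**Assumptions (mine).** Two-sided alpha 0.05, exact test. A feature has the same true prevalence f in implant and normal fields, and the two fields are independent unless stated. The documents give no prevalence, so 20% and 30% are illustrative.

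**Step 1: rejection threshold with one-way discordance.** With c implant-only pairs and none the other way, exact p = 2 × 0.5^c.
- c = 5: p = 0.0625
- c = 6: p = 0.031

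Six pairs are enough.

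**Step 2: relative rule.** The implant is aberrant if the feature is present there and absent in the paired normal field, so q = f(1 − f). The probability of rejecting is P(Bin(n, q) ≥ 6).

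| f | q | 30 pairs | 20 pairs |
|---|---|---|---|
| 30% | 0.3 × 0.7 = 0.21 | 0.625 | 0.230 |
| 20% | 0.2 × 0.8 = 0.16 | 0.345 | 0.087 |

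There is no true difference in any row.

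**Step 3: sensitivity.**
- *Correlated fields.* The fields lie side by side, so positive correlation is plausible. With phi = 0.3 and f = 30%, q = 0.21 × (1 − 0.3) = 0.147, giving about 27% (30 pairs) and 6% (20 pairs).
- *Where 5% is crossed.* Rejection exceeds 5% only when q passes 0.091 (30 pairs) or 0.140 (20 pairs). Under the relative rule these correspond to f of about 10% (0.101 × 0.899 = 0.091) and 17% (0.168 × 0.832 = 0.140).
- *Test version.* The uncorrected chi-square equals c when discordance is one-way, so it rejects from c = 4 (4 > 3.84). The inflation would be larger.

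**Step 4: both fields scored, but reading is differential.** Suppose 10% of normal and 30% of implant fields are called aberrant with no true difference. The discordant probabilities are 0.1 × 0.7 = 0.07 and 0.3 × 0.9 = 0.27. Summing the exact test's rejection region over all discordant counts gives 0.358 (30 pairs) and 0.188 (20 pairs). A milder 10% against 20% gives 0.096 and 0.042.

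**Step 5: the comparator.** With one absolute rule for both fields and no differential reading, each discordant cell has probability f(1 − f). For f from 5% to 50%, the exact test rejects with probability 0.0015 to 0.028 (30 pairs) and 0.0002 to 0.023 (20 pairs).

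**The case against.** The strongest reply is that the text does not force one-way discordance. Tortuosity, closed loops and disorganised branching can be scored in any field. Normal tissue need not mean the paired field, and the density and flow criteria in the same list use a standard deviation, which may point to a reference distribution. Naming McNemar's test for normal-versus-aberrant variables also presupposes that both members are rated. This stands. The plan is ambiguous, and a reader should not infer that a significant result is guaranteed.

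A reader might also take the feature's full prevalence in the implant as the discordance rate while fixing the normal field at zero. At 30% prevalence that gives P(Bin(30, 0.3) ≥ 6) = 92%, or 58% with 20 pairs. The documents do not support this as the consequence of a relative rule: an implant beside equally tortuous peritoneum is not aberrant in comparison with it. The figures in Step 2 are the ones that follow.

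Nor is the whole first secondary endpoint in doubt. Its listed measures in Section 3.3 are diameter, density, dye detection and flow. Structure and branching are not among them, although Section 9 tests them.

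Finally, scoring rules may exist in the cited preclinical work, which cannot be checked here, and the study is openly unblinded. Neither point fills the gap: the plan states no common rule for the two fields, and an open-label design does not prevent masked reading of recorded video.

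**Conclusion.** The concern holds conditionally. As written, Section 9 permits a scoring rule under which McNemar's test is not valid, and it describes no protection against unmasked reading.

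If the paired normal field is the reference, the false-positive rate is about 62% (30 pairs) or 23% (20 pairs) at an assumed 30% prevalence, and 35% or 9% at 20%. If both fields are scored but reading is differential at 10% against 30%, it is 36% or 19%. These figures rest on an assumed alpha, the exact test, independent fields and chosen prevalences. With low prevalence or correlated fields, the inflation shrinks and can vanish.

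The problem is confined to the structure and branching comparisons. Dye detection is rated present or absent without reference to normal tissue and does not share the definitional problem. The paired t tests and the primary feasibility endpoint are not affected.

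**What to change.** In Section 9:
- Remove the comparison with normal tissue from criteria 1 and 2.
- State that every implant field and every normal field is scored separately by the same absolute criteria, for example closed loop present yes or no, and tortuosity by a fixed rule set before reading.
- State that the existing reader scores coded clips in random order without the tissue label, and that the label is restored only for the McNemar test.

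The videos are already recorded and stored, so no extra patients, procedures or readers are needed. The cost is a few sentences and some clip-coding work. Tissue type may sometimes still be recognisable on screen, so masking will be imperfect; the common absolute rule is worth having regardless.
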